#### Demographic and Laboratory Assessments

- 2. Adult **male or female**, between 18 and 75 years of age, inclusive, at time of the Baseline visit.
- 3. **Laboratory values** meeting the following criteria within the screening period prior to the first dose of study drug:
  - Serum aspartate transaminase (AST) and alanine transaminase (ALT)  $\leq 2 \times$  upper limit of normal (ULN);
  - Total white blood cell (WBC) count  $\geq 3.0 \times 10^9/\text{L}$ ;
  - Absolute neutrophil count (ANC)  $> 1,200 \text{ cells}/\mu\text{L}$ ;
  - Absolute lymphocyte count (ALC)  $> 750 \text{ cells}/\mu\text{L}$ ;
  - Total bilirubin  $< 2 \text{ mg/dL}$ , except for subjects with isolated elevation of indirect bilirubin relating to Gilbert's syndrome;
  - Estimated glomerular filtration rate (GFR) by simplified 4-variable Modification of Diet in Renal Disease (MDRD) formula  $\geq 40 \text{ ml/min}/1.73 \text{ m}^2$ ;
  - Hemoglobin  $\geq 9 \text{ g/dL}$ ;
  - Platelet count  $\geq 100,000/\mu\text{L}$ .
- 4. Are willing or able to comply with procedures required in this protocol.

- ✓ 5. Subject must not have an active, chronic, or recurrent infection that based on the Investigator's clinical assessment makes the subject an unsuitable candidate for the study, or the following:
  - Subject must not be currently infected with *C. difficile* toxin as identified during Screening or another known intestinal pathogen.
  - Subject must not be infected with human immunodeficiency virus (HIV)
  - Subject must not have active hepatitis B or hepatitis C (as defined in [Appendix F](#))
  - Subject must not have active tuberculosis (TB). Subjects with a positive QuantiFERON TB / or Purified Protein Derivative (PPD) skin test during Screening may participate in the study if further workup (including a mandatory chest X-ray [CXR] and other testing according to local country guidelines) establishes conclusively that the subject has no evidence of active TB. If latent TB is established, the subject must initiate and complete a minimum of 2 weeks (or per local guidelines, whichever is longer) of an ongoing TB prophylaxis/treatment or have documented completion of a full course of TB prophylaxis, prior to Baseline. Subjects with active TB or a history of active TB who have documented completion of a full course of anti-TB therapy may be allowed to enter the study after consultation with the AbbVie Therapeutic Area Medical Director (TA MD).
  - Confirmed COVID-19: the Baseline visit must be at least 14 days from onset of signs/symptoms or positive SARS-CoV-2 test; symptomatic subjects must have recovered, defined as resolution of fever without use of antipyretics and improvement in symptoms;
  - Suspected COVID-19: subjects with signs/symptoms suggestive of COVID-19, known exposure, or high risk behavior should undergo molecular (e.g., PCR) testing to rule out SARS-CoV-2 infection or must be asymptomatic for 14 days from a potential exposure.

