## 5 STUDY ACTIVITIES

### 5.1 Eligibility Criteria

---

Subjects must meet all of the following criteria in order to be included in the study. Anything other than a positive response to the questions below will result in exclusion from study participation.

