## Tuberculosis (TB) Testing/TB Prophylaxis

All subjects must be evaluated for TB at Screening and annually. The TB screening tests provide diagnostic test results to be interpreted in the context of the subject's epidemiology, history, exam findings, etc., and it is the responsibility of the Investigator to determine if a subject has previous, active, or latent TB. Expert consultation for the evaluation and/or management of TB may be considered per Investigator discretion.

At screening, all subjects will be assessed for evidence of increased risk for TB by a risk assessment form ([Appendix C](#)) and tested for TB infection by QuantiFERON-TB Gold test or purified protein derivative (PPD) test. The site staff will complete the TB risk assessment form and enter the data into the appropriate eCRF. The TB risk assessment questionnaire will be completed annually (Part I only) for all subjects, regardless of TB test results.

If a subject had a negative purified protein derivative (PPD) test within 90 days prior to Screening and a QuantiFERON-TB Gold test cannot be performed by Central Lab at Screening and source documentation is available, TB testing by PPD Skin Test does not need to be repeated, provided nothing has changed in the subject's medical history to warrant a repeat test. These cases may be discussed with the AbbVie TA MD. The results of the TB test(s) will be retained at the site as the original source documentation.

Subjects with a negative TB test may be enrolled. Subjects with a positive TB test must be assessed for evidence of active TB versus latent TB, including signs and symptoms and CXR. Subjects with no signs or symptoms and a CXR not suggestive of active TB may be enrolled after initiation of TB prophylaxis. Subjects with evidence of active TB must not be enrolled.

Any positive TB test after a subject with a negative test at Baseline has started the study should be reported as an AE of latent TB or active TB (as applicable).

If the subject is experiencing signs or symptoms suspicious for TB or something has changed in the subject's medical history to warrant a repeat test, the case (including the TB test results) must be discussed with the AbbVie TA MD.

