#### TB Prophylaxis

At screening, if the subject has evidence of latent TB infection, prophylactic treatment must be initiated at least 2 weeks prior to administration of study drug (or per local guidelines, whichever is longer). At least 6 months of prophylaxis need to be completed. However, the full course of prophylaxis does not need to be completed prior to the first dose of study drug.

Of note, Rifampicin or Rifapentine is not allowed for TB prophylaxis.

Subjects with a prior history of latent TB that have documented completion of a full course of anti-TB therapy will be allowed to enter the study provided nothing has changed in the subject's medical history

to warrant repeat treatment. For subjects with completion of a full course of anti-TB therapy, but insufficient documentation, the investigator should consult with the AbbVie TA MD.

During the study, subjects with new evidence of latent TB should initiate prophylactic treatment immediately per local guidelines and complete at least 6 months of prophylaxis. TB prophylaxis should be initiated and study drug(s) should not be withheld. The subject should be re-evaluated (unscheduled visit) for signs and symptoms as well as laboratory assessment of toxicity to TB prophylaxis 2 to 4 weeks later. Newly initiated prophylactic treatment and prior therapy should be captured in the eCRF.

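### Criterion 5 bars active TB but, in its last sentence, lets subjects named as having active TB enter after a documented full course and sponsor consultation; for active disease despite a completed course, this conflicts with its own opening and with the Operations Manual.

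*Protocol*

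**What the plan says.** Protocol Section 5.1 requires every criterion to be met: "Anything other than a positive response to the questions below will result in exclusion from study participation".

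The TB bullet of criterion 5 makes three statements that bear on active disease:

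- It opens with "Subject must not have active tuberculosis (TB"), and attaches no condition.
- A subject with a positive TB test may take part only if further workup "establishes conclusively that the subject has no evidence of active TB".
- It closes with "Subjects with active TB or a history of active TB who have documented completion of a full course of anti-TB therapy may be allowed". That route is open only once the sponsor's medical director has been consulted.

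The Operations Manual (Protocol Appendix F) covers the same ground twice. Section 3.12, under Tuberculosis (TB) Testing/TB Prophylaxis, states: "Subjects with evidence of active TB must not be enrolled". Footnote b to the visit activities in Section 2.1 lets a subject with a positive or repeatedly indeterminate test take part only if the workup is negative for active TB. Neither place gives an exception for completed therapy.

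**The concern.** One bullet forbids a condition and then names the same condition among those that may be admitted, and the Operations Manual sides with the prohibition. Protocol Section 8.2 requires the study to follow both the protocol and the Operations Manual, so a site cannot settle the matter by choosing one document.

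The rule concerns safety. Protocol Section 2.2 states that the drug may impair immune function and raise the risk of infection, including opportunistic infection. Section 6.1 lists active TB as its own adverse event of special interest. Approximately 35 sites are to apply the criterion. There is also a reporting consequence: SAP Appendix A counts subjects who entered without satisfying the entry criteria, and for the case in question the text does not settle whether such a subject is a deviation.

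**Working it through.** No arithmetic applies, and the plan gives no figure on this point. The check applies each rule to each kind of subject.

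| Subject at screening | Criterion 5, opening | Criterion 5, last sentence | Operations Manual 3.12 and 2.1 footnote b | Conflict |
|---|---|---|---|---|
| Active TB, no completed course | Barred | No route, since a documented full course is required | Barred | None |
| Active TB now, despite or after a documented full course; sponsor consulted | Barred | May be allowed | Barred | Yes |
| Past active TB, documented full course, no current evidence of disease | Not barred | May be allowed after consultation | Not barred, since only evidence of active TB is excluded | None |

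Only the second row produces opposite answers. Three readings might remove the conflict:

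1. **The last sentence is an exception to the opening one.** Criterion 5 would then be consistent with itself. The Operations Manual would still bar the same subject, with no matching exception.
2. **The opening sentence governs, and the last sentence cannot override it.** Criterion 5 would then agree with the Operations Manual, but the reference to active TB in the last sentence would have no effect.
3. **Active TB in the last sentence means a past, treated episode.** Nothing would then conflict. But the sentence names a history of active TB separately, joined by the word or, so its first term would be redundant. The documents elsewhere keep the categories apart: Operations Manual 3.12 asks the investigator to distinguish previous, active and latent TB, and footnote e of the maintenance schedule in Protocol Appendix D speaks of prior active TB when it means past disease.

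The third reading is the likeliest intent, but the text does not say so. The first and second are both open to a site reading literally, and they lead to different decisions.

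**The case against.** The strongest reply is that this is loose drafting of two or three words inside a sentence with two safeguards. The requirement for a documented full course qualifies both groups named, and the decision passes through one sponsor medical director, so sites are not left to their own discretion. Operations Manual 3.12 also asks for sponsor contact before enrolling anyone whose chest X-ray suggests previous TB. All of this stands, and it makes a wrongly enrolled subject unlikely. It does not say which sentence governs when the director is consulted about a subject with current disease.

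Three stronger readings are tempting, and the documents do not support them.

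- **That untreated active TB may enter.** A reader who takes the phrase without its conditions might infer this. Criterion 5 gives no such route.
- **That treated past TB is also caught in a contradiction.** Operations Manual 3.12 excludes only evidence of active TB. Appendix D footnote e, and the annual testing rule in Operations Manual 3.12, both contemplate enrolled subjects with a TB history. The Operations Manual states no entry rule for past active TB, but it does not forbid entry.
- **That the documents contradict each other on proof of treatment.** Operations Manual 3.12, under TB Prophylaxis, says: "For subjects with completion of a full course of anti-TB therapy, but insufficient documentation, the investigator should consult" the sponsor's medical director. That sentence directly follows one on prior latent TB, so setting it against the active-TB sentence of criterion 5 compares different groups. For latent TB, criterion 5 accepts ongoing prophylaxis "or have documented completion of a full course of TB prophylaxis, prior to Baseline". Advice to consult about an incomplete record grants no entry and does not clearly contradict a documentation requirement.

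**Conclusion.** The inconsistency is real but narrow. It affects a subject with current active TB who has a documented full course of therapy behind them and whose case has been put to the sponsor. For that subject the opening of criterion 5 and both Operations Manual passages say no, and the last sentence of criterion 5 says possibly.

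The documents give no count; the number of such subjects is probably very small. A reader might put a size on it by supposing that one pre-existing case would add 1/40 = 2.5% to the active TB row of the special-interest table. That figure is not supported. SAP Section 9.2.1 defines treatment-emergent events by onset on or after the first dose, so disease present before dosing would not ordinarily count. SAP Section 9.2.6 does not repeat that limit, but nothing there says that pre-existing disease is included. Moreover, 40 is the approximate enrolment target, not a stated Safety Analysis Set denominator. The requirement in Protocol Section 6.2 to stop drug governs TB that develops on study and does not settle entry.

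The point is an internal inconsistency in a safety eligibility rule. It has no bearing on the primary endpoint, the placebo prior, the sample size or the primary analysis. The conclusion rests on reading the current text literally; if only treated past disease was meant, the defect is one of wording, but it still needs correcting because the wording says something else.

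**What to change.** Reconcile the last sentence of criterion 5 with its opening sentence, with the enrolment bar in Operations Manual 3.12, and with footnote b of Operations Manual 2.1. The result should be one rule, stated the same way in each place, that covers current active TB and previously treated active TB as separate cases and says whether completed therapy and sponsor consultation change the answer for either. Which rule applies is for the sponsor's clinical team to decide. The cost is a few words in criterion 5 and, if needed, matching words in the Operations Manual. No analysis, sample size or SAP text changes.

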### Disease Activity

- ✓ 6. Diagnosis of UC for at least 3 months prior to Baseline. Appropriate documentation of biopsy results consistent with the diagnosis of UC in the assessment of the Investigator, must be available.
- ✓ 7. Subject meets the following disease activity criteria: Active UC with an Adapted Mayo score of 5 to 9 points and endoscopic subscore of 2 to 3 (confirmed by central review).
- ✓ 8. No current diagnosis of CD or inflammatory bowel disease-unclassified (IBD-U).
- ✓ 9. No extent of inflammatory disease limited to the rectum as assessed by screening endoscopy.
- ✓ 10. No currently known complications of UC such as:
  - fulminant colitis,
  - toxic megacolon,
  - previous colectomy (total or subtotal),
  - or any other manifestation that might require surgery while enrolled in the study
- ✓ 11. Subjects must not have an ostomy or ileoanal pouch.

## Subject History

- ✓ 12. History of inadequate response, loss of response, or intolerance to one or more of the following:
  - Demonstration of intolerance requires no minimum dose or duration of use.
  - Inadequate response is defined as outlined below:
    - Signs and symptoms of persistently active disease despite a history of one or more of the following:
      - Infliximab: At least one 6-week induction regimen of infliximab ( $\geq 5$  mg/kg intravenous [IV] at Weeks 0, 2, and 6),
      - Adalimumab: At least one 4-week induction regimen of adalimumab (one 160 mg SC dose at Week 0, followed by one 80 mg SC dose at Week 2),
      - Golimumab: At least one 4-week induction regimen of golimumab (200 mg SC at Week 0 and 100 mg SC at Week 2),
      - Vedolizumab: At least one 6-week induction regimen of vedolizumab (300 mg IV at Weeks 0, 2, and 6),
      - Tofacitinib: At least one 8-week induction regimen of tofacitinib (10 mg PO twice a day) or
      - Ustekinumab: At least an induction regimen of a single weight-based infusion dose of ustekinumab (260 mg IV with body weight [bw]  $\leq 55$  kg, 390 mg with bw  $> 55$  kg to 85 kg, 520 mg with bw  $> 85$  kg).
    - Recurrence of symptoms during scheduled maintenance dosing following demonstration of clinical benefit of the above biologics or tofacitinib.
- ✓ 13. No history of radiation or ischemic colitis.
- ✓ 14. No history of **any malignancy** except for successfully treated non metastatic cutaneous squamous cell or basal cell carcinoma or localized carcinoma in situ of the cervix.
- ✓ 15. No history of clinically significant (per investigator's judgment) **drug or alcohol abuse** within the last 12 months.
- ✓ 16. No history of clinically significant medical conditions or any other reason that the investigator determines would **interfere with the subject's participation** in this study or would make the subject an unsuitable candidate to receive study drug.
- ✓ 17. No history of **dysplasia** of the gastrointestinal tract or evidence of dysplasia in any biopsy performed during the Screening endoscopy, other than completely removed low-grade dysplastic lesions (historically or during Screening).
- ✓ 18. No history of **lymphoproliferative disease**, including lymphoma, or signs and symptoms suggestive of possible lymphoproliferative disease, such as lymphadenopathy and/or splenomegaly.
- ✓ 19. No history of an **allergic reaction** or significant sensitivity to excipients of the study drug or the ingredients of Chinese hamster ovary (CHO) cells.

- 20. No severe, progressive, or uncontrolled renal, hepatic, hematological, endocrine, disorder or symptoms thereof.

## Contraception

- 21. For all females of childbearing potential, a **negative serum pregnancy test** at the Screening Visit and a negative urine pregnancy test at baseline prior to the first dose of study drug. Procedures in the case of a borderline serum pregnancy test are described in [Appendix F](#).
- 22. Female subjects of childbearing potential must practice at least 1 protocol-specified **method of birth control** (Section 5.2), that is effective from Study Day 1 through at least 84 days after the last dose of study drug. Female subjects of non-childbearing potential do not need to use birth control.
- 23. Females must not be **pregnant, breastfeeding, or considering becoming pregnant** during the study or for at least 84 days after the last dose of study drug.

## Concomitant Medications

- 24. Subject must not receive IV anti-infectives within 35 days prior to Baseline visit or oral/intramuscular (IM) anti-infectives (non-UC-related) within 14 days prior to the Baseline visit.
- 25. Subject must not receive any parenteral nutrition within 35 days prior to Baseline.
- 26. Subject must not receive cannabis for either recreational or for medical reasons within 14 days prior to Baseline.
- 27. Subject must not receive cyclosporine, tacrolimus, or mycophenolate mofetil (unless for ocular application) within 35 days prior to Baseline.
- 28. Subject must not receive fecal microbial transplantation within 35 days prior to Baseline.
- 29. Subject must not have been treated with **any approved biologic agent** (e.g., infliximab, adalimumab, golimumab, vedolizumab) within 8 weeks prior to Baseline, or with tofacitinib within 14 days prior to Baseline, or any investigational biologic or other agent or procedure within 35 days or 5 half-lives prior to Baseline, whichever is longer. Subject must not have been treated with ravagalimab at any time prior to Baseline.

Note: If there is proper documentation of an undetectable drug level measured by a commercially available assay for any of the approved biologics above, there is no minimum washout prior to Baseline.

- 30. Subject must not have received **any live vaccine** within 35 days prior to Baseline.
- 31. Subject must not receive oral UC-related antibiotics or oral aminosalicylates within 14 days prior to Baseline unless they have been on stable doses for greater than 14 days prior to Baseline.

- ✓ 32. Subjects must not have received oral corticosteroids, unless they have been on that corticosteroid for at least 14 days prior to Baseline and on a stable dose for at least 7 days prior to Baseline. Subjects taking oral corticosteroids must not be taking oral corticosteroids at the following doses: budesonide > 9 mg/day, beclomethasone > 5 mg/day, prednisone or equivalent > 20 mg/day.
- ✓ 33. Subject must not be on immunomodulators (azathioprine [AZA], mercaptopurine [6-MP], methotrexate [MTX]) unless they have been on the course for at least 42 days prior to Baseline and have been on a stable dose for at least 35 days prior to Baseline.
- ✓ 34. Subject must not receive the following therapies within 14 days prior to Screening or during Screening:
  - A combination of 2 or more of the following: oral budesonide, oral beclomethasone, and/or oral prednisone (or equivalent) simultaneously, with the exception of inhalers
  - IV corticosteroids
  - Therapeutic enema or suppository (i.e., rectal aminosalicylates/corticosteroids), other than required for endoscopy
- ✓ 35. Subject must not have received apheresis (e.g., Adacolumn apheresis) within 60 days prior to Screening or during Screening.

## 5.2 Contraception Recommendations

---

### Contraception Requirements for Females

Subjects must follow the following contraceptive guidelines as specified:

- Females, Non-Childbearing Potential

Females do not need to use birth control during or following study drug treatment if considered of non-childbearing potential due to meeting any of the following criteria:

- Postmenopausal, age > 55 years with no menses for 12 or more months without an alternative medical cause.
- Postmenopausal, age ≤ 55 years with no menses for 12 or more months without an alternative medical cause AND a follicle-stimulating hormone (FSH) level > 40 IU/L.
- Permanently surgically sterile (bilateral oophorectomy, bilateral salpingectomy, or hysterectomy)

- Females, of Childbearing Potential

Females of childbearing potential must avoid pregnancy while taking study drug and for at least 84 days after the last dose of study drug. Females must commit to one of the following methods of birth control:

- Combined (estrogen and progestogen containing) hormonal birth control (oral, intravaginal, transdermal, injectable) associated with inhibition of ovulation initiated at least 30 days prior to study Baseline Day 1.

- Progestogen-only hormonal birth control (oral, injectable, implantable) associated with inhibition of ovulation initiated at least 30 days prior to study Baseline Day 1.
- Bilateral tubal occlusion/ligation (can be via hysteroscopy, provided a hysterosalpingogram confirms success of the procedure).
- Intrauterine device (IUD).
- Intrauterine hormone-releasing system (IUS).
- Vasectomized partner (provided the partner has received medical confirmation of the surgical success of the vasectomy and is/are the sole sexual partner(s) of the trial subject).
- Practice true abstinence, defined as: Refraining from heterosexual intercourse when this is in line with the preferred and usual lifestyle of the subject (periodic abstinence [e.g., calendar, ovulation, symptothermal, post-ovulation methods] and withdrawal are not acceptable).

If required per local practices, male or female condom with or without spermicide OR cap, diaphragm or sponge with spermicide should be used in addition to one of the birth control methods listed above (excluding true abstinence).

Contraception recommendations related to the use of concomitant therapies should be based on the local label.

